#### 22.2 Safety Analyses

The safety analysis data set will contain all participants that are registered and commenced trial treatment (received at least one dose of Anakinra).

#### 23 Baseline Characteristics

Descriptive statistics will be reported overall. Categorical data will be summarised by frequency and percentages with the denominator as the number registered. Continuous data will be summarised by mean, standard deviation (SD), median, inter-quartile range (IQR), minimum and maximum.

Patient demographics are to be summarised as follows from Form 1:Screening:

- Age (years)
- Age categorised for EudraCT
  - Adults (18-64 years)
  - o From 65 to 84 years
  - o 85 years and over
- Sex
- o Male
- o Female
- Ethnicity
  - Arab
  - Asian Other
  - Bangladeshi
  - Black African
  - o Black Caribbean
  - Black Other
  - Chinese
  - Gypsey or Irish Traveller
  - Indian
  - o Irish
  - Other ethnic group

- Other mixed
- Other white
- Pakistani
- White and Asian
- White and Black African
- o White and Black Caribbean
- o White British
- Clinical chemistry/Hepatic functions tests\*
  - o Sodium
  - Potassium
  - o Urea
  - Creatinine
  - Biblirubin
  - o ALT
  - Alkaline Phosphatase
  - GGT
- Haematology Tests\*
  - o Full Blood count
  - o Full Blood count differential
  - Neutrophil count
  - Neutrophil count result (10^9/L)

\*All Clinical chemistry/Hepatic functions tests and Haematology Tests will be summarised with the categories Normal, Abnormal NCS and Abnormal CS as collected on the CRF (bar the Neutrophil count result which is numeric).

The below patient demographics are collected on both Form 1 Screening and Form 2 Baseline, summaries should be provided for Form 2 but if missing the value on Form 1 should be used:

Vital signs

- Height [cm]
- Weight [kg]
- Heart rate [bpm]
- Blood pressure [mmHg]

Limb volume

• Limb volume (Lower) [cm]

LCTC\_ST003\_TEMP1: SAP Template, V0.1, 08/01/2021 (developed using LCTC\_GE001\_TEMP4: LCTC Template of a Template, V1.0, 04/09/2020)

CLINICAL TRIALS CENTRE LCTC

Limb volume (upper) [cm]

Average pain score over last 24 hours:

At baseline

Research blood samples:

Consent to blood samples (Yes/No)

Blood sample taken (Yes/No)

**24** Compliance with Interventions

Exposure to treatment will be assessed by mean dose (mg) per participant. Dosing is once daily for a

maximum of 120 days; the mean and median number of doses per participant over the treatment

period (expressed as number of days treatment administered for) will be summarised.

Compliance of treatment will be captured by summarising the number of returned used syringes

compared to non-used syringes. The number of syringes used is detailed on the Accountability Log.

The number of syringes dispensed will also be summarised as detailed on the Accountability log.

Compliance will be further categorised as: more than expected (1 or more additional doses), less than

expected (at least one fewer than expected) and as expected (exact number expected taken)

according to the doses taken and expected.

25 Analysis of Outcomes

25.1 Interim Reporting

25.1.1 For reports to independent oversight committees

No formal interim analyses of primary or secondary outcomes will be performed but analyses of the

accumulating data (recruitment, protocol deviations, baseline characteristics, compliance,

withdrawals, missing data and safety data) will be performed at regular intervals (at least annually)

for review by an IDSMC.

Recruitment will be summarised as stated in Section 19. The number of patients lost to follow-up, the number still being followed-up successfully and number who have completed follow up will be presented. Alongside the completeness of data collected in relation to primary and secondary outcomes as detailed in the trial protocol. A summary of baseline characteristics as stated in Section 23 will also be provided. Compliance to treatment (as defined in Section 24) and visits will be reported. Compliance for treatment will be split into the following 30 day timepoints for reporting to the IOC: day 30, day 60, day 90 and day 120.

The IDSMC will also review the progression criteria for the INCA study.

25.1.2 Assessment of progression criteria

25.1.2.1 Recruitment

The recruitment rate will be calculated across the first 6 months of trial overall and by site as:

[total number registered]/[number of months open to recruitment]

If the average recruitment rate per site per month is 0.5 or more this criteria has been met.

25.1.2.2 Safety

The frequency and proportion of participants, denominator used as the number registered, who have experienced the below will be summarised:

persistent pain (greater than one week) at the injection site of at least moderate intensity (≥

5 on a 0-10 NRS scale)

• a substantial CRPS pain increase of  $\geq$  2 points NRS, ongoing for more than 1 month despite

and from the time of pain related treatment stop.

SARs

The substantial pain increase will be calculated as: CRPS pain at day X – CRPS pain at day (X-30), where X is >30. Persistent pain will be derived from the pain dairies and adverse events. Both substantial pain increase and persistent pain are collected throughout the trial as Adverse events and are particularily asked about at each visit (see forms 5 – Telephone Follow up, 6 Follow up and 7 Final Telephone follow up). The yes/no response at each visit and the derived substantial pain increase/persistent pain will

both be used to ensure all events are captured.

If 3 or less patients report persistent pain or substantial pain increase across the first 10 participants

registered this criteria will have been met.

However, stopping will be considered if 30% or more of study participants experience an SAR in the first 12 months of recruitment.

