11 PROGRESSION CRITERIA

Monitoring for clinical trial progress will focus on recruitment and safety. This will be done by the IDSMC.

The following factors will be used to inform the decision to progress into the next stage of the trial:

- 1. **Recruitment**. Assessed 6 months from recruitment start. Initial recruitment rate of 0.5 participants each month per centre for the first 6 months from recruitment start.
- 2. **Safety**. Assessed 12 months from recruitment start (or later if it takes longer for 10 participants to be registered): For the first 10 registered participants, 3 or less reporting persistent pain (greater than 1 week) at injection site of at least moderate intensity (5 or greater on a 0-10 NRS scale) or substantial CRPS pain increase (>=2points NRS), ongoing for >1 month despite and from the time of pain-related treatment stop.
- 3. **Safety**. Assessed 12 months from recruitment start: Consider stopping if 30% or greater of study participants experiencing a serious adverse reaction (SAR).
- 4. **Recruitment and adherence**: At 12 months from recruitment start to have at least 12 participants registered and at least 50% of registered participants completing their active treatment.
- 5. **Futility**. After 12 participants have been recruited and completed 4 months treatment period, an average of no pain increase among completed participants (to visit 5/ 120 day) and at least one participant reporting at least 2 points of pain reduction on the NRS (rounded to the nearest whole number), both these criteria referring to the average pain recordings over the last two weeks before visit 5 / 120 day compared to baseline (0 day).

The IDSMC will use the above progression rules as a guide during regular monitoring with regards to trial progress and will provide a recommendation to the TSC concerning continuing the study. The above are not intended as strict stop/start criteria.

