14.2.1 Feasibility of Sample Size

Between the two recruiting sites we expect a recruitment rate of one patient every month (across the two centres) for the first 6 months from commencing recruitment. In the second 12 months recruitment rate will be expected to be two patients monthly across both sites.

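### The month-12 SAR proportion counts every registered participant whatever their exposure, so at planned accrual it understates SAR risk per 120-day course by about 1 to 7 percentage points at a true 30%.

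*SAP*

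**What the plan says.** Protocol section 11 lists, as its third progression criterion, a safety check 12 months after recruitment starts: stopping is to be considered if at least 30% of study participants have had a SAR. SAP 18.1.2 repeats it. SAP 25.1.2.2 gives the calculation: "The frequency and proportion of participants, denominator used as the number registered, who have experienced the below will be summarised". SARs are one of the listed items. The decision sentence is "stopping will be considered if 30% or more of study participants experience an SAR in the first 12 months of recruitment".

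Neither document requires a minimum time on drug for this check, or plans an exposure-adjusted or time-to-event estimate. By contrast, the futility criterion in the same list waits until 12 participants have been recruited and have completed the 4-month treatment period.

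On accrual, Protocol 14.2.1 says "we expect a recruitment rate of one patient every month (across the two centres) for the first 6 months from commencing recruitment" and then "In the second 12 months recruitment rate will be expected to be two patients monthly across both sites". The treatment course is 120 days (Protocol section 3). Criterion 4 sets a lower bound: "At 12 months from recruitment start to have at least 12 participants registered".

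**The concern.** A participant registered a week before the month-12 cut has had almost no opportunity for a SAR, yet adds one full unit to the denominator. Recruitment is planned to double after month 6, so a large share of the cohort is in this position when the check is made. If the committee reads the 30% limit as a tolerable risk for a course of treatment, the crude proportion will tend to sit below that risk.

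This is the only progression criterion that attaches a number to SARs. Criterion 2 concerns injection-site pain and CRPS pain, and the ground of an unacceptable safety profile in Protocol 10.10 carries no figure. A figure that leans in the reassuring direction is therefore worth correcting.

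**Working it through.** **Accrual.** 6 months × 1 + 12 months × 2 = 30, which reproduces the stated sample size and supports reading the second rate as starting at month 7. At month 12 this gives 6 + 6 × 2 = 18 registered. Since 0.30 × 18 = 5.4, the limit is reached at 6 participants with a SAR.

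**Exposure at month 12.** Place entries at the middle of each recruitment interval, with 30.44 days per month. Ten participants have at least 120 days. The other eight have about 114, 99, 84, 68, 53, 38, 23 and 8 days, a total of 487 days or 487/120 = 4.06 courses. The cohort has accrued (10 + 4.06)/18 = 78% of 18 full courses. With entries at the start of each interval, 11 have a full course and the figure is 81%; at the end, 10 and 75%.

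**Expected proportion shown.** This is the mean over the 18 participants of F(t), the probability of a SAR by exposure time t, with F(120 days) = 30%. The documents give no SAR timing, so it is an assumption and was varied. With mid-interval entry:

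- Uniform over 120 days: 0.30 × 0.781 = 23.4%.
- Constant hazard, F(t) = 1 − 0.7^(t/120): the ten completers contribute 3.00 and the other eight 1.29, so 4.29/18 = 23.8%.
- All within the first month: only the last two entrants are short, with 0.75 and 0.25 of a month, so 0.30 × (16 + 0.75 + 0.25)/18 = 28.3%.

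**Chance of reaching 6 of 18 at a true 30%.** Exact Poisson-binomial probabilities; ranges cover the three entry patterns.

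| SAR timing (assumed) | Expected shown | Chance of reaching the limit |
|---|---|---|
| Uniform over 120 days | 22.6-24.3% | 20-25% |
| Constant hazard over 120 days | 23.0-24.6% | 21-27% |
| Half in the first 28 days | 24.3-26.0% | 26-32% |
| All within 60 days | 25.9-27.5% | 31-37% |
| All within 28 days | 27.6-29.2% | 37-44% |
| Full exposure of all 18 | 30% | 47% |

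Under uniform timing, the true risk would have to be about 37-40% for the expected figure to reach 30%. At a true 40%, the chance of reaching the limit is 52% (uniform) or 54% (constant hazard), against 79% with full exposure. If SARs were spread over the 180-day follow-up instead, the expected figure at a true 30% would be about 19-21.5%.

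**With 12 registered** (1 per month, 4 SARs needed): uniform or constant hazard gives 23.8-26.6%. If all SARs fall within 28 days the range is 27.5-30.0%, the upper end being no dilution at all. The chance of reaching the limit runs from 31% to 51%, against 51% with full exposure.

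Dropout was not modelled.

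**The case against.** The strongest objection is that the target is inferred. Protocol section 11 speaks of a share of study participants at a calendar date, and the SAP computes exactly that. Neither document mentions risk per course. This stands: the SAP follows the protocol's wording, and the point is about what the figure can be taken to mean.

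A reader might infer that a true 30% SAR risk would simply be waved through. The documents do not support that. Section 11 says the criteria are a guide and not strict stop/start rules; the IDSMC recommends and the TSC decides. At the same look the IDSMC sees safety data, compliance at days 30, 60, 90 and 120 (SAP 25.1.1) and the number completing treatment (SAP 25.1.2.3), so it can tell that many participants are part-exposed. Protocol 10.10 also provides for suspension on suspicion of unacceptable risk.

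Nor is the whole shortfall due to dilution. With full exposure of all 18, a true 30% still falls below the limit 53% of the time, because 6 of 18 is 33%. Dilution adds about 3 to 27 percentage points. The larger values need SARs spread across the course. The only timing statement, in Protocol 5.2.1, is that most AEs appear at 4 weeks. It concerns AEs in general, but it points to the milder end.

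Two further inferences add almost nothing. The SAP's dosed safety set (22.2) differs from the registered set, but Protocol 10.6 has participants start on the day of registration, so the two will nearly coincide. The SAP counts SARs in the first 12 months without dating the denominator, but Protocol section 11 and SAP 18.1.2 date the whole check at 12 months.

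**Conclusion.** The point holds as a limited one. At planned accrual the crude SAR proportion understates the per-course risk: a true 30% is expected to show as about 23-29%, near 28% if SARs occur in the first month. The chance of reaching the limit is about 21-44% instead of 47%. Incomplete exposure cannot raise the expected proportion, but its effect can shrink to nothing with slow accrual and early onset, so it would be wrong to say the check is always biased. The size rests on three assumptions: the Protocol 14.2.1 accrual, an assumed SAR time profile, and reading 30% as a per-course risk. What is affected is a guide figure for the IDSMC, which does not by itself decide whether the trial continues.

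**What to change.** In SAP 25.1.2.2, keep the 30% figure and the crude count over registered participants. Add beside them, at the same data cut, a Kaplan-Meier estimate of first SAR to day 120 among dosed participants, and the person-months of treatment accrued, for the IDSMC to read against 30%. State how participants who stop treatment early without a SAR are censored. In simulation with the accrual above, constant hazard and a true 30%, this estimate averages about 30% and reaches the limit 48% of the time, close to the 47% with full exposure.

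Do not use a denominator of those who completed, stopped or had a SAR. It admits recent participants only if they had an event or stopped, and a true 30% then shows as about 37.5% (constant hazard) or 41.6% (first-month onset). Restricting to participants with a full 120 days is unbiased but fragile: at a true 30%, the chance of staying below the limit is 38% with 10 such participants (3 needed) and 57% with 11 (4 needed).

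The cost is a sentence or two in the SAP and one line in the IDSMC report. Dosing records and SAE onset dates are already collected. The estimate is less precise than one from 18 fully followed participants, and Protocol section 11 may need a matching clarification.

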There is considerable variation in the duration of anakinra therapy in many of the indications above. CRPS is a chronic condition that can be present for many years. Many of the studies in RA used a duration of 12-24 weeks. Familial periodic fever was 4 months and gout was only for days as the natural history for acute attacks are very short.

4 months was chosen for anakinra in CRPS as we wanted to determine primarily safety and tolerability. Most AEs are seen at 4 weeks and can last 14-28 days. 4 months will allow for observation and follow up of adverse effects and to enable patients to observe the benefits of rehabilitation if anakinra has beneficial effects on pain and function.

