^{**} Additional pregnancy tests may be conducted during the participation of the trial if there is any suspicion of being pregnant

^{***} Type of Clinical assessment will be only completed if at a visit. If completed by phone no clinical assessment will take place

[~] May be taken at earlier timepoint if participant withdraws before day 120.

⁺ unblinded QST

[#] Study Completion

All follow up visits will be scheduled from baseline (Day 0). Each participant will complete treatment administration from day 0 to day 120 and will be followed up for 180 days in total. During this time, scheduled follow ups will be conducted via both telephone as well as clinic visits. No face to face study visits are planned after 120 days.

Following registration each participant will be given a diary that they will fill in and record their pain intensity in accordance with the schedule:

- Weekly between day 0 to day 90
- Daily Between day 90 to day 120
- Weekly between day 120 to day 180

Clinic Follow-Up Visits:

Participants will need to attend clinics for follow-up at 30, 60, 90 and 120 days. These visits should be arranged at the baseline visit post registration. The following data should be collected and assessments/activities performed at all visits (unless specified differently below):

- Concomitant medication
- AEs
- Further Provision of Anakinra
- Collection of safety blood samples
- Collection of research blood samples (30ml, day 120 only)
- · Clinical assessment and examinations including:
 - o Pain assessment on NRS from their pain diaries
 - o Limb Volume (days 60 and 120 only)
 - o Vital signs: BP, HR, and weight

Telephone follow ups:

Research nurses (RNs) will telephone participants approximately 2 weeks (+/-3 days) after each clinic visit up to day 120 when the last drug dose is administered, and a final telephone follow up at day 180 at the end of the trial. Telephone appointments will be arranged and conducted by local research teams. The following information should be collected and recorded on the appropriate CRF:

- Concomitant medication
- AEs
- Pain assessment up to 120 days at the end of drug administration (NRS)
- EQ5D-5L questionnaire at day 180

Efficacy Assessments

This trial is not designed to determine efficacy, however data will be collected on outcomes that will be used to determine efficacy in a future definitive trial. Outcomes are detailed in section 9.

Safety Assessments

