#### 18.1.2 Assessments of progression criteria

See section "Progression criteria" of the INCA protocol. Assessment of the clinical trial progress will focus on the recruitment and safety of the study, which will be assessed by the IDSMC.

- Recruitment\*. Initial recruitment rate of 0.5 participants each month per centre for the first 6 months from recruitment start.
- Safety\*\*¹. For the first 10 registered participants, ≤3 reporting persistent pain (>1 week) at injection site of at least moderate intensity (≥5 on a 0-10 NRS scale) or substantial CRPS pain increase (≥2points NRS), ongoing for >1 month despite and from the time of pain-related treatment stop.
- Safety\*\*. Consider stopping if ≥30% of study participants experience a serious adverse reaction (SAR).

- 4. Recruitment and adherence\*\*: At least 12 participants registered and ≥50% of registered participants completing their active treatment.
- 5. **Futility**. After 12 participants have been recruited and completed the 4 months treatment period, an average of no pain increase among completed participants (to visit 5 (120 day)) and at least one participant reporting at least 2 points of pain reduction on the NRS (rounded to the nearest whole number), both these criteria referring to the average pain recordings over the last two weeks before visit 5 (120 day) compared to baseline (0 day).

\*Assessed 6 months from recruitment start. \*\* Assessed 12 months from recruitment start.¹or later if it takes longer for 10 participants to be registered).

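### The SAP's derived flag for a substantial CRPS pain increase, a moving 30-day difference, does not implement the event that the protocol and SAP define

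*SAP*

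**What the plan says.** Protocol section 11, item 2, defines the pain part of the first safety criterion as "substantial CRPS pain increase (>=2points NRS), ongoing for >1 month despite and from the time of pain-related treatment stop". SAP 18.1.2 repeats the duration and anchor ("ongoing for >1 month despite and from the time of pain-related treatment stop"), and a bullet in SAP 25.1.2.2 states them again.

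SAP 25.1.2.2 then gives the calculation: CRPS pain at day X minus "CRPS pain at day (X-30), where X is >30". It adds that both harms are also collected as adverse events and asked about at each visit. On combining the sources it says "The yes/no response at each visit and the derived substantial pain increase/persistent pain will" "both be used to ensure all events are captured". The criterion is met on this condition: "If 3 or less patients report persistent pain or substantial pain increase across the first 10 participants".

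Diary entries are scheduled "Weekly between day 0 to day 90", then daily to day 120, then weekly to day 180 (Protocol 10.7). Each follow-up time point has a window of 3 days either way. Protocol section 11 calls the criteria a guide for the IDSMC and says they are not meant as strict rules.

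**The concern.** The definition has three parts: a rise of at least 2 points, a duration of more than a month, and a clock that starts at pain-related treatment stop. The calculation is one difference between two readings 30 days apart, against a reference that moves with X. Because X must exceed 30, day 0 is never the reference. By contrast, the same SAP uses the Form 4 day 0 score for futility (25.1.2.4) and for change in pain (25.2.3.2.1.1).

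The count feeds the only numeric progression threshold for condition-specific harm that the IDSMC receives, since item 3 concerns serious adverse reactions only. A flag built on a different event can mislead in both directions: it can count transient change as harm, and it can be silent on worsening that began in the first month.

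**Working it through.** The documents give no error rate for this criterion, so there is no figure of theirs to reproduce.

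**Inputs from the documents.** Formula: D(X) = pain(X) − pain(X−30), X > 30, with the 2-point threshold taken from the event definition. Clinic visits: days 30, 60, 90, 120. Telephone calls: about days 14, 44, 74, 104. Pairs of scheduled contacts 30 days apart therefore exist at X = 44, 60, 74, 90, 104, 120, and pairs of clinic visits at X = 60, 90, 120.

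**Step 1: fixed patterns, no assumption about variability.**

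| Pain pattern | Any X, 31 to 180 | Scheduled contacts | Clinic visits |
|---|---|---|---|
| 6 to 8 on day 1, kept | none | none | none |
| 6 to 8 on day 7, kept | X = 31–36 | none | none |
| 6 to 8 on day 14, kept | X = 31–43 | none | none |
| 6 to 8 on day 20, kept | X = 31–49 | day 44 | none |
| Linear 6 to 8 over 120 days | none | none | none |
| 6-4-6 (4 on day 30 only) | X = 60 | day 60 | day 60 |
| 6-8-6 (8 on day 60 only) | X = 60 | day 60 | day 60 |

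For the linear rise, D = 2 × 30/120 = 0.5 throughout. For 6-4-6, D(60) = 6 − 4 = 2, although pain never exceeds its starting level. For 6-8-6, D(60) = 8 − 6 = 2, although the rise has gone by the next reading.

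**Step 2: can the difference carry the duration?** For a lasting step on day t, D is non-zero only when X ≥ t and X − 30 < t, that is t ≤ X ≤ t + 29. It spans at most 30 days. Asking D itself to stay at 2 or more for longer than 30 days would exclude every lasting 2-point step. Duration must be judged against a fixed reference.

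**Step 3: data fit.** Assume weekly entries on days 7, 14, and so on. Since 30 = 4 × 7 + 2, no two weekly entries are exactly 30 days apart. The first exact diary pair is day 93 with day 63 (9 × 7). Visit windows also break exact spacing. The SAP names neither the readings nor a tolerance.

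**Step 4: stable patients.** The following are assumptions, not in the documents: 200,000 simulated patients with no true change; means about 7.2, limited to 6–9; scores rounded to whole numbers and limited to 0–10; independent readings; within-patient SD as shown. A patient is flagged if any single D is 2 or more. Then P(4 or more of 10) = 1 − Σ(k = 0 to 3) C(10,k) p^k (1−p)^(10−k).

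| SD | Flagged, clinic visits | P(≥4 of 10) | Flagged, all contacts | P(≥4 of 10) |
|---|---|---|---|---|
| 0.5 | 7% | 0.4% | 14% | 4% |
| 0.75 | 25% | 22% | 44% | about 70% |
| 1.0 | 42% | 66% | 66% | 98% |

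For example, at p = 0.25: 1 − (0.0563 + 0.1877 + 0.2816 + 0.2503) = 0.224. With serial correlation of 0.3 per 14 days, the clinic-visit rates are 6%, 23% and 40%.

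**Step 5: a rule closer to the definition.** Require at least 2 points above day 0 at every scheduled contact over a span of more than 30 days. False flags fall to 0.3%, 1.9% and 4.6% at the same SDs, and at SD 1.0 the chance of 4 or more of 10 is below 0.1%. With a 7-day pre-baseline mean as reference, the rate at SD 1.0 is 0.03%. The treatment-stop clause was not modelled.

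**The case against.** The strongest reply is that the formula carries no threshold. It may give only the size of the rise, while the bullet above it gives the event, duration included. On that reading the Step 4 figures do not apply, and the fair criticism is that duration is left without a rule. This has force, and the figures are therefore conditional on counting each single difference. It does not rescue the text. The SAP presents the difference as the way the event is calculated and supplies no duration or treatment-stop rule. Step 2 shows that the difference cannot carry the duration, and the day 1 step has no non-zero difference on any reading.

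Other points that stand:

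- A reader might infer that early sustained worsening goes uncounted. The documents do not support that. The yes/no items and adverse event reports are a second source, with contacts at two weeks and day 30. The miss belongs to the derived flag alone.
- Nor does the formula miss every early rise at every X. A 3-point rise on day 10 gives D = 3 at X = 31 to 39 and is missed only at scheduled contacts.
- It is tempting to cite Protocol 5.2.1, "Most AEs are seen at 4 weeks and can last 14-28 days", as proof that the blind period is where these harms fall. Events lasting 14–28 days would not meet a requirement of more than a month, so that sentence does not help.
- The event wording names no reference. A fixed baseline is the sensible choice and matches the SAP's other pain derivations, but the definition does not spell it out.

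The second source does not cure the false flags: using both sources to capture all events adds events and removes none.

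**Conclusion.** The derived flag is wrong as written: it measures a different event from the one defined. That conclusion rests on the texts and the fixed patterns and needs no assumption about variability.

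The size of the false-flag problem does rest on assumptions. If each single difference of 2 or more counts, clinic-visit flags in stable patients run from about 7% at SD 0.5 to 42% at SD 1.0, and the chance of reaching 4 of 10 runs from 0.4% to 66%. The documents give no within-patient SD, so the problem could be small or large.

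Two stronger readings are not supported. The count does not decide continuation: it informs an IDSMC recommendation under criteria that the protocol calls a guide. And an effect on the primary outcome is not shown: SAP 25.2.2.1 shares the event concept but relies on CRF indications and does not cite this formula.

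**What to change.** Replace the formula in SAP 25.1.2.2 with a derivation that does the following:

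- Takes a rise of at least 2 NRS points over a fixed pre-treatment baseline. Use the Form 4 day 0 score, as in SAP 25.1.2.4 and 25.2.3.2.1.1, with the pre-baseline diary mean as a sensitivity analysis.
- Requires the rise to be sustained over readings that span more than 30 days, with the first 30 days of treatment included.
- Names the diary or visit readings to be used and their windows.
- Applies the treatment-stop anchor of the protocol's own definition for criterion 2.
- States how an isolated lower reading or a missing reading is handled, so that one low score does not silently cancel a harm.

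Keep CRF yes answers and adverse event reports as events in their own right. Overruling them with the derivation could delete harms that participants reported. Report derived and reported counts separately as well as combined, so that the IDSMC sees any disagreement. Use the same derivation to support the primary outcome, which has no derivation of its own for this event.

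The cost is SAP wording and programming, since all readings are already scheduled. The limitation is that persistence before day 90 rests on weekly diary entries and scheduled contacts.
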